## **8.3 Reporting**

### **8.3.1 Reporting of SAE**

All SAEs occurring throughout the entire course of the trial have to be reported to the CRO DS Department. The CTS has to send the completed SAE form by e-mail or fax to the CRO DS Department within 24 hours of becoming aware of the AE.

SAE should be faxed to the following number:

[figure not shown]
**Chiltern Drug Safety**  
**[contact]**  
**[contact]**  
**email: [contact]**

The investigator should not delay reporting because of missing information. Nonetheless, the report should be as complete as possible. This initial notification should include, as a minimum, sufficient information to permit identification of the following:

- the reporter (investigator's name and contact information)
- the subject
- involved trial medication
- AE(s)
- Seriousness criterion and/or criterion for AESI
- date of onset

The CRO DS Department alerts BN DS of all SAEs and provides the available information within 24 hours to BN DS. BN is responsible for expedited as well as periodic reporting to the involved regulatory authorities (e.g. FDA, PEI) according to applicable laws and guidelines. Regulatory authorities will be notified as soon as possible but no later than 7 days after first knowledge of fatal or life-threatening unexpected SAE with an at least possible relationship to the IMP (serious adverse drug reaction [SADR]) and no later than 15 days after knowledge of any other unexpected SADR. In addition BN will report the SAEs to the responsible Biomedical Advanced Research and Development Authority (BARDA) representative when applicable and forward them to the DSMB, while the investigator or the CRO is responsible for reporting to the IECs or IRBs.

[Figure 2](#) outlines the reporting process and timelines SAEs.

**Figure 2: Algorithm for Reporting of SAEs**

[figure not shown]
### **8.3.2 Reporting of AESI**

All AESIs occurring throughout the entire course of the trial have to be reported to the CRO DS Department. The CTS has to send the completed AESI form by e-mail or fax to the CRO DS Department within 24 hours of becoming aware of the AE.

AESIs should be faxed to the following number:

Chiltern Drug Safety  
[contact]  
[contact]  
email: [contact]

A periodic report for AESIs will be provided from the CRO to BN DS. [Figure 3](#) outlines the reporting process and timelines for AESIs.

**Figure 3: Algorithm for Reporting of AESIs**

### 8.3.3 Reporting of Pregnancies

If a subject becomes pregnant during the active trial period (up to and including one month [minimum 28 days] after receiving a dose of vaccine) this must be reported to BN on a Pregnancy Report Form within 24 hours of the investigator's becoming aware of the event.

A pregnancy should be followed to term, any premature terminations reported, and the health status of the mother and child including date of delivery and the child's gender and weight should be reported to BN after delivery.

Any event during pregnancy fulfilling the criteria for an SAE will be reported as SAE to CRO/BN DS. However, hospitalization for delivery is a prospectively planned hospitalization and is not considered a SAE per se.

## 9 Statistical Considerations

### 9.1 Primary Trial Hypothesis

The primary hypothesis of the trial is to show that the humoral immune responses after IMVAMUNE® vaccination are statistically equivalent. The humoral immune response is defined per group as the GMT of a group measured by PRNT at Visit 4. The trial should demonstrate that the means of the log10 titers are equivalent within a pre-specified amount. This amount is called the margin of equivalence ( $\Delta$ ).

Suppose  $m_1$  is the mean of the log10 titers in Group 1,  $m_2$  is the mean of the log10 titers in Group 2 and  $m_3$  is the mean of the log10 titers in Group 3. The test on equivalence will be applied for the following hypothesis:

$$H_0: m_1 - m_2 \leq -\Delta \text{ OR } m_1 - m_2 \geq \Delta \text{ OR } m_1 - m_3 \leq -\Delta \text{ OR}$$

$$m_1 - m_3 \geq \Delta \text{ OR } m_2 - m_3 \leq -\Delta \text{ OR } m_2 - m_3 \geq \Delta$$

versus

$$H_1: m_1 - m_2 > -\Delta \text{ AND } m_1 - m_2 < \Delta \text{ AND } m_1 - m_3 > -\Delta \text{ AND}$$

$$m_1 - m_3 < \Delta \text{ AND } m_2 - m_3 > -\Delta \text{ AND } m_2 - m_3 < \Delta$$

$\Delta$  is the margin of equivalence and is chosen to be 0.301 for the log10 titers of the PRNT (this is equivalent to a factor of 2 for the GMT).

From previous experience it is anticipated that the standard deviation (SD) for the log10 titers for PRNT in the IMVAMUNE® groups is 0.85.

The above hypothesis will be tested based on the difference of the log10 titer means being approximately normally distributed (which has been shown to be a very good approximation in all previous IMVAMUNE® studies). Specifically, the lower and upper one-sided 97.5% confidence interval limits for the difference of log10 means will be calculated. If all of the lower confidence interval limits for  $m_1 - m_2$ ,  $m_1 - m_3$  or  $m_2 - m_3$  are above  $-\Delta$  and all of the lower confidence interval limits for  $m_1 - m_2$ ,  $m_1 - m_3$  or  $m_2 - m_3$  are below  $\Delta$  the null-hypothesis will be rejected in favor of the alternative hypothesis of equivalence.

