## 1.5 Protocol Synopsis

Title	A randomized, double-blind, placebo-controlled Phase III trial to evaluate immunogenicity and safety of three consecutive production lots of IMVAMUNE ® (MVA-BN ® ) smallpox vaccine in healthy, vaccinia-naïve subjects.
Clinical phase	Phase III
Sponsor	Bavarian Nordic A/S [name] [name], Denmark
Coordinating Investigator	[name] [name]. Division of Infectious Diseases University of Alabama at Birmingham [name] [name] [name], USA
Number of clinical trial sites and country/ies	Up to 40 in the United States of America (USA)
Vaccination dose and schedule	Two vaccinations four weeks apart (at Day 0 and Day 28) with either 0.5 ml IMVAMUNE ® vaccine containing a nominal titer of $1 \times 10^8$ TCID 50 (standard dose) or 0.5 ml placebo (Tris-buffered saline, TBS).
Route of administration	Each IMVAMUNE ® vaccination / placebo administration consists of one subcutaneous (s.c.) injection.
Trial duration	Up to 39 weeks for each subject.
Sample size	4,000 (1,000 subjects per group).

---

Primary objective	To assess the consistency of three consecutively produced IMVAMUNE ® lots.
-------------------	---

---

Secondary objectives	
To assess uncommon adverse reactions, in particular any cardiac sign and symptom indicating a case of myo-/pericarditis, and to compare the frequency of those reactions against placebo.
 
To collect vaccinia-specific humoral immune response data.

----------------------	--

---

Primary endpoint	Geometric Mean Titers (GMTs) after two IMVAMUNE ® vaccinations measured by Plaque Reduction Neutralization Test (PRNT) at trial Visit 4.
------------------	---

---

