#### 4.2.2 Active Trial Phase

After successfully passing the screening assessments the eligible subject will enter the active trial phase (Visit 1 to Visit 5) starting with Visit 1.

Randomized treatment assignments for the subjects will be done at Visit 1 after re-confirmation of subject's eligibility. The randomization scheme is 1:1:1:1 (three IMVAMUNE® production lot groups and one placebo group). Randomization will be stratified by CTS. An automated randomization system will be used. The detailed process will be described in a trial specific charter.

The procedures performed at Visit 1 and all following visits are listed below. **Blood draws and all other examinations listed above the vaccination events must always be performed prior to vaccination.**

At Visit 1 / Day 0, subjects will receive the first of two s.c. vaccinations with one standard dose of IMVAMUNE® (0.5 ml vaccine containing a nominal titer of  $1 \times 10^8$  TCID50) or placebo containing TBS in the non-dominant upper arm (deltoid region).

Following vaccination, subjects will be kept under close observation by the CTS staff for at least 30 minutes with appropriate medical treatment readily available in case of an unexpected anaphylactic reaction following administration of the vaccine. Any AEs that occur during or after vaccination will be recorded.

Reactogenicity and AEs will be collected on a subject memory aid by having the subject record daily maximum temperatures and solicited AEs for an 8-day period (Days 0-7), beginning with the day of vaccination. The memory aid will be returned to the clinic staff at the following visit. If symptoms persist at Day 7, daily symptoms and temperature will continue to be measured each day until resolved and the last day of symptoms and maximum intensity is recorded on the memory aid. AEs will be assessed at all active trial period visits (Visit 1 to Visit 5).

Visit 1 (Day 0)

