## 7 Assessment of Immunogenicity

Immune response analyses are planned at trial Visit 4. The baseline assessment for immunogenicity parameters will be performed on samples taken at trial Visit 1 (before first vaccination). It is planned that antibody serum samples will be taken from all subjects, however only samples from the first 700 subjects per group will be analyzed for immunogenicity endpoints. The remaining samples will be stored for potential future use (see [section 7.2](#)).

The methods of collection, storage and handling of lab specimens for immune analysis are specified in the Central Laboratory's Manual, which will be provided to the investigators before enrollment commences. Additionally, training will be provided on the procedures during the Investigator Meeting and/or at the initiation visit.

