## 9.3 Sample Size Calculation

### Primary objective

The primary objective of the trial is to demonstrate equivalence of three consecutively produced lots of IMVAMUNE® in terms of humoral immunogenicity in vaccinia-naïve subjects after two doses. Assuming a significance level of 5%, an analyzable sample size of 600 in each group for the per protocol set, and an expected log10 titer SD of 0.85 in all groups for the PRNT, then the primary hypothesis of the GMT based on the PRNT at Visit 4 (i.e. after two IMVAMUNE® vaccinations) has a power of >80% of showing equivalence for all three IMVAMUNE® groups, using an equivalence margin of  $\Delta=0.301$  on the log10 scale.

In order to account for a dropout rate of about 15%, which has been observed in previous IMVAMUNE® trials, blood will be analyzed from a total of 700 subjects in each group.

In order to allow a proper safety analysis as described in the sections below, 300 additional subjects will be enrolled in each group to ensure that a total of 1,000 subjects per group are available.

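### Randomisation is stratified by site, but the confirmatory lot-equivalence limits in section 9.1 are stated as plain differences of group means with no site term: valid, at most slightly conservative, and cheap to align

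*Protocol*

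**What the plan says.** **Design.** Protocol section 4.2.2: "Randomization will be stratified by CTS". For allocation, "The randomization scheme is 1:1:1:1", that is, three lots and placebo. The synopsis (section 1.5) gives the number of sites as "Up to 40 in the United States of America (USA"). No other stratification factor is named.

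**Confirmatory analysis.** Section 9.1 sets m1, m2 and m3 as the means of the log10 PRNT titres in the three lot groups, with the response taken at Visit 4. It then gives the calculation: "Specifically, the lower and upper one-sided 97.5% confidence interval limits for the difference of" the log10 means. Delta "is the margin of equivalence and is chosen to be 0.301 for the" log10 PRNT titres. The section names no model, no site term and no variance estimator. Section 9.4 places all confirmatory testing on the per protocol set.

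**Planning and deferral.** Section 9.3 plans on 600 analysable subjects per lot and an SD of 0.85, with no allowance for site. Section 9.5 leaves the full analysis details to a SAP, which is not at hand.

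**The concern.** Stratifying by site keeps the lots nearly balanced within each site, so differences between sites largely cancel in the lot contrasts. If the standard error is then computed from the spread of titres around the plain group means, that between-site spread is still in it. It then overstates the true sampling variability of the contrast, and the limits cover more often than their nominal level.

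What is at stake is modest. The lot GMT ratios and their limits are the trial's main result, and they would be reported a little less precisely than the design allows. Section 9.1 also states the confirmatory contrast specifically enough that a SAP using a site-adjusted model would describe a different calculation from the protocol.

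**Working it through.** **Inputs.** From sections 9.1 and 9.3: n = 600 per lot, SD = 0.85, margin 0.301, 97.5% one-sided limits. Section 9.3 says "Assuming a significance level of 5"%, read here as two-sided, which matches those limits. The share of variance explained by site, R², is not in the protocol, so a range is assumed.

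**1. The plan's own figure.** SE of a pairwise difference = 0.85 × sqrt(2/600) = 0.0491. With equal lots, pairwise power = 2Φ(0.301/0.0491 − 1.96) − 1 ≈ 99.997%. For all three pairs jointly, the Bonferroni bound is 1 − 3 × 0.00003 = 99.99%, and simulation of three group means (400,000 runs) agrees. The stated power above 80% is therefore met with a wide reserve.

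**2. Half-width as stated.** 1.96 × 0.0491 = 0.0962 log10, a GMT-ratio factor of 10^0.0962 = 1.248, or 32% of the margin.

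**3. Half-width with a site term.** The residual SD becomes 0.85 × sqrt(1 − R²), so the half-width is 0.0962 × sqrt(1 − R²). The last column is simulated joint power when one lot truly lies 0.15 log10 from the other two.

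| Assumed R² for site | Half-width (log10) | GMT-ratio factor | Joint power, one lot 0.15 away |
|---|---|---|---|
| 0 | 0.0962 | 1.248 | 78.4% |
| 0.01 | 0.0957 | 1.247 | 78.9% |
| 0.05 | 0.0937 | 1.241 | 80.9% |
| 0.10 | 0.0912 | 1.234 | 83.4% |
| 0.20 | 0.0860 | 1.219 | 87.9% |
| 0.30 | 0.0805 | 1.204 | 92.4% |

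At R² of 5% to 10% the limits narrow by 0.002 to 0.005 log10, that is by 2.5% (1 − sqrt 0.95) to 5.1% (1 − sqrt 0.90).

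**4. Effect on the decision.** The largest observed difference that passes is 0.301 − 0.0962 = 0.205 log10. With site fitted it is 0.301 − 0.0937 = 0.207 or 0.301 − 0.0912 = 0.210. Joint power with equal lots stays at about 99.99%.

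**5. Cost in degrees of freedom.** Three lots of 600 give 1,800 subjects. Lot alone leaves 1,800 − 3 = 1,797 residual degrees of freedom; adding 39 site terms leaves 1,758. The loss is negligible.

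**The case against.** The strongest reply is that nothing here is an error. An unadjusted comparison after stratified randomisation is unbiased, and its wider limits make equivalence harder to claim, not easier. It matches the GMT definition in section 7.1 and the total SD used in section 9.3. Model terms are commonly left to the SAP, and section 9.5 defers to one that may already include CTS. Site may also explain very little: under section 7.1 all PRNT assays are run at one laboratory by blinded staff. All of this stands, and it limits the point to a recommendation. It does not remove the point, because section 9.1 goes beyond silence: it defines plain group means and says which differences receive limits.

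A reader might infer that the limits are definitely wider than the design supports. The protocol gives no variance share for site, so that holds only conditionally.

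A reader might also infer that the baseline titre must be adjusted for, since "The baseline assessment for immunogenicity parameters will be performed on samples taken at trial Visit 1". The documents do not support making this part of the core point:

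- Entry is restricted to vaccinia-naive subjects, and section 7.1 codes titres below the cut-off as 1 (log10 = 0). Most baselines should therefore be the same constant.
- If 1% to 2% of subjects had a baseline titre of 10 to 20, carried through with slope 1 (assumptions), baseline would explain only about 1% to 5% of the variance.
- If 2% were seropositive (assumption), the SD of the between-lot difference in that proportion is sqrt(2 × 0.02 × 0.98/600) = 0.008. With a Visit 4 titre 1 log10 higher in such subjects (assumption), that shifts a lot difference by about 0.008 log10, under 3% of the margin. The interval already covers chance imbalance of this kind.

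**Conclusion.** The point holds as a minor recommendation. Section 9.1 does not carry the trial's only stated stratification factor into the confirmatory limits. The analysis is valid, and if site explains any variance it is slightly conservative. The size is about 0.002 to 0.005 log10 on a half-width of 0.0962, assuming site explains 5% to 10% of the variance, and nothing if it explains none. These figures also assume that the lots stay close to balanced within site among the subjects analysed.

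The point does not mean that the trial is underpowered or that false equivalence becomes more likely. With equal lots the gain is precision of the reported ratios. Power improves noticeably only if a lot truly differs while remaining inside the margin, as in the last column of the table.

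**What to change.** State in section 9.1 that the three pairwise lot differences and their one-sided 97.5% limits come from a linear model of log10 Visit 4 PRNT titre with lot and CTS as factors. Small sites should be pooled by a rule written down before unblinding. Keep the unadjusted difference of log10 means as a sensitivity analysis. If the SAP already specifies such a model, only the wording of section 9.1 needs to be aligned with it.

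The cost is a sentence or two of text and one model. The one real downside is having to devise the pooling rule. The sample size does not change. A Visit 1 titre covariate may be added as an option; its slope would rest on the few subjects who are seropositive at baseline.

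### The primary equivalence rule tests the lower confidence limits twice and never the upper limits, so lots that differ two-fold or more in one direction can pass as consistent

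*Protocol*

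**What the plan says.** Section 9.1 (Primary Trial Hypothesis) defines equivalence for the pairwise differences m1−m2, m1−m3 and m2−m3 of mean log10 PRNT titers at Visit 4. The alternative hypothesis requires each difference to lie above −Δ and below +Δ. Δ "is the margin of equivalence and is chosen to be 0.301", and the section adds that "this is equivalent to a factor of 2 for the GMT".

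The section then has "the lower and upper one-sided 97.5% confidence interval limits for the difference" calculated for each pair. The decision rule that follows has two clauses:

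- The first begins "If all of the lower confidence interval limits for" the three differences and requires them to be above −Δ.
- The second continues "and all of the lower confidence interval limits for" the same three differences and requires them to be below +Δ.

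If both clauses are met, "the null-hypothesis will be rejected in favor of the alternative hypothesis of equivalence".

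No other section of the Protocol restates or corrects this rule. Section 9.3 gives only the margin, the SD, the number per group and the power. The list of changes in section 17.5.2 does not touch section 9.1.

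**The concern.** A test of equivalence by confidence limits needs the lower limit above −Δ and the upper limit below +Δ. The second clause names the lower limit again. A lower limit below +Δ is no evidence that the true difference is below +Δ. It only fails to show that the difference exceeds +Δ. The upper half of the two one-sided tests is therefore missing.

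Lot consistency is the primary objective. Section 9.4 bases all confirmatory testing on the per protocol set, and section 9.5 treats tests of secondary endpoints as descriptive, so this is the only confirmatory decision rule in the trial. Taken literally, it has two defects:

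- It does not control the risk of calling inconsistent lots consistent when a lower-numbered lot is the higher one.
- The verdict depends on lot numbering. A high Lot 1 can pass where an equally deviant low Lot 1 fails.

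**Working it through.** **Inputs.** Margin Δ = 0.301 and one-sided 97.5% limits (section 9.1); 600 analyzable subjects per group and "titer SD of 0.85 in all groups for the PRNT" (section 9.3). Normal approximation with the SD taken as known.

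**Standard error and half-width.** SE = 0.85 × √(2/600) = 0.0491. Half-width = 1.96 × 0.0491 = 0.0962.

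**The Protocol's own power figure.** Section 9.3 claims more than 80% for all three lots and gives no assumed true difference; zero is assumed here. Under the two-limit rule, power for one pair = 2Φ(0.301/0.0491 − 1.96) − 1 = 0.99997. For three pairs jointly it is at least 1 − 3 × (1 − 0.99997) = 0.9999, and simulation gives the same. The stated figure holds.

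**What each rule accepts for one pair.**

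- Literal rule, lower limit between −Δ and +Δ: observed difference from −0.301 + 0.096 = −0.205 to 0.301 + 0.096 = 0.397. The upper end is a GMT ratio of 10^0.397 = 2.50, with an upper confidence limit of 0.397 + 0.096 = 0.493, or 3.11-fold.
- Two-limit rule: observed difference from −0.205 to 0.301 − 0.096 = +0.205, or at most 1.60-fold either way.

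**One pair at a true difference of exactly +Δ.** The literal rule passes if the observed difference is below Δ + 1.96 × SE. That has probability Φ(1.96) = 0.975, where the intended value is 0.025.

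**All three pairs together.** Three lot means were simulated and both rules applied to the same draws. The table gives the percentage of trials that declare equivalence.

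| True means, Lots 1, 2, 3 (log10) | Largest gap | Literal rule | Two-limit rule |
|---|---|---|---|
| 0.301, 0, 0 | 2-fold | 95 | 0.5 |
| 0.301, 0.1505, 0 | 2-fold | 97 | 2.5 |
| 0.35, 0, 0 | 2.24-fold | 73 | 0.01 |
| 0.35, 0.175, 0 | 2.24-fold | 83 | 0.2 |
| 0.398, 0, 0 | 2.5-fold | 33 | about 0 |
| 0.398, 0.199, 0 | 2.5-fold | 49 | about 0 |
| −0.301, 0, 0 | 2-fold, Lot 1 low | 0.5 | 0.5 |
| 0, 0.1505, 0.301 | 2-fold, Lot 3 high | 2.5 | 2.5 |

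The last two rows show that the −Δ side is controlled under both rules.

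**Effect of the correction on power.** Under the two-limit rule, with the middle lot halfway between the other two, joint power is 98.3% at a true spread of 0.10 log10 and 86.5% at 0.15 log10.

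**The case against.** The strongest reply is that this is a slip of one word and not a choice of analysis. Section 9.1 states the two-sided hypotheses, says those hypotheses are what will be tested, and has upper limits calculated that serve no other purpose. A statistician would read the second clause as meaning the upper limits. Section 9.5 leaves full details to an analysis plan finalized before database lock, and that plan, which was not available for this check, may state the rule correctly. The high pass rates describe the sentence as printed, not how the trial would most likely be analysed. They also arise only when a lower-numbered lot is the higher one, and at 2.5-fold the faulty clause already stops half or more of trials.

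All of this stands as a description of intent and likely risk. It does not make the sentence right. The Protocol's criterion and its hypothesis disagree, and if Lot 1 or Lot 2 came out high the two readings could give opposite verdicts on the primary endpoint. Choosing between them after the data are known is what a pre-specified rule should prevent. Amendment 1 reports a review of the whole protocol for formal consistency and corrects a reference year in section 9.3, yet the error remained.

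**Conclusion.** The decision rule in section 9.1 is wrong as written. It omits the upper limits and contradicts the hypotheses in the same section. If applied literally, its rate of false equivalence at the +Δ boundary is about 95% to 97%, where the two-limit rule gives at most 2.5%. It would accept an observed GMT ratio of up to nearly 2.5-fold. The −Δ side is unaffected.

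These figures rest on 600 per group, an SD of 0.85 in every lot and the normal approximation. The cause is almost certainly a wording error. It still must be fixed, because it sits in the trial's sole confirmatory criterion. Margin, sample size and power claim all stand.

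**What to change.** In the second clause of the rule, replace *lower* with *upper*, so that it requires the upper limits of m1−m2, m1−m3 and m2−m3 all to be below Δ. An equivalent wording is that the two-sided 95% confidence interval of each pairwise difference must lie wholly between −0.301 and +0.301. Changing *or* to *and* in the two lists of differences would read better but is optional, since the clauses already speak of all the limits.

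Confirm that the analysis plan and its programs use the same two-limit rule before database lock.

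The cost is small but not zero. Under section 15 an amendment needs written approval by the coordinating and site investigators and must go to all participating investigators. Under section 10.2 the ethics committees must be informed. There are up to 40 sites. No trial procedure or sample size changes.
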